### **5.2 RESPONSE CRITERIA**

#### **5.2.1 Immunologic Response Criteria**

Immunologic responses to TARP peptide vaccination will be assessed at weeks 0, 12 (after 3 vaccines), 18 (after 5 vaccines), 24, 36, 48, 60 and 96; Note: apheresis will be performed at weeks 0, 24, 48 and 96. Refer to [Appendix 3](#) for details of specimen tube, collection and

processing and to [Appendix 4](#) for descriptions of the immunology assays. Additional exploratory analyses of TARP immunologic responses will be performed at Weeks 60, 72, 96, 108, 120, 132 and 144.

A positive immunological response to class I TARP peptides is defined as:

- A three-fold increase over baseline in the number of positive cells by tetramer staining  
**OR**
- A three-fold increase over baseline in the number of positive cells by IFN- $\gamma$  ELISPOT assay.
- Positive assays must be confirmed at two study time points to be considered a definitive, vaccine-induced positive result.
- Week 24 immunologic *responders* will be allowed to receive an additional dose of TARP peptide vaccine at Week 36.
- The study time points at which a positive immunologic response is documented will be noted for every patient enrolled on the study.

Hence a patient will be considered a responder if they demonstrate a positive response as described above in either the tetramer or the IFN- $\gamma$  ELISPOT assays.  $^{51}\text{Cr}$  release cytotoxic T lymphocyte (CTL) assays using T2 cells as targets will only be performed in patients documented to have a positive tetramer or ELISPOT response and will not be utilized in the assessment of immunologic response.

A positive  $^{51}\text{Cr}$  release CTL assay will be defined as:

- The percent lysis observed against TARP peptides is at least 2 standard deviations greater than the percent lysis observed against control peptides AND
- Greater than or equal to a 10% difference in the TARPT peptide percent lysis vs. control peptide percent lysis at more than one effector to target cell ratio.

### 5.2.2 PSADT Response Criteria

PSADT was chosen as a surrogate marker for biochemical response to vaccination based on the Prostate-Specific Antigen Working Group's consensus Guidelines on PSADT. Utilization of PSADT as a predictive factor of disease progression and prostate cancer death is based on level II evidence derived from cohort- or case-controlled analytic studies or controlled, non-randomized trials that have been validated in multiple data sets, PSADT will be calculated using the Memorial Sloan-Kettering Cancer Center cancer information prostate nomogram for PSA doubling time found at:

<http://www.mskcc.org/mskcc/shared/forms/Nomograms/flash/load.cfm?type=Prostate&width=586&height=505&title=Prostate%20Nomogram> recommended in the Prostate Specific Antigen Working Group Guidelines. The PSADT is calculated assuming an exponential increase in serum PSA and first order kinetics. The formula takes into account the natural logarithm of 2 divided by the slope obtained from fitting a linear regression of the natural log of PSA on time. All PSA values used in the calculation should be 0.20 ng/ml or greater and follow an increasing trend. PSA values need not be consecutively increasing and all values obtained during a maximum period of 12 months prior to a given protocol time point will be included in the calculation. The maximum period of the last 12 months is recommended to reflect current disease activity because in some men PSADT may change over time. Multiple studies concur that men with a PSADT < 3 months are at extremely high risk for metastatic disease progression

and death with prostate cancer mortality approaching 100%; for this reason they have been excluded from participation in this study. In contrast, men with a slow PSADT i.e. > 15 months have an extremely low risk of death from prostate cancer.

The following general guidelines regarding PSA determinations and calculation of PSADT used in this protocol will be adhered to (refer to [Appendix 5](#), PSADT Calculation Guidelines)

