## **2 ELIGIBILITY ASSESSMENT AND ENROLLMENT**

### **2.1 ELIGIBILITY CRITERIA**

#### **2.1.1 Inclusion Criteria**

- 2.1.1.1 Males  $\geq$  18 years of age with histologically confirmed adenocarcinoma of the prostate.
- 2.1.1.2 HLA-A\*201 positive
- 2.1.1.3 Patients must have
  - 2.1.1.3.1 Completed and recovered from all prior definitive therapy (surgery, brachytherapy, cryotherapy or radiotherapy) for the primary tumor, or other definitive-intent local therapy.
  - 2.1.1.3.2 Stage D0 disease with documented biochemical progression documented by a rising PSA.
  - 2.1.1.3.3 No evidence of metastatic disease by physical examination, CT scan or bone scan.
  - 2.1.1.3.4 For patients following definitive radiation therapy or cryotherapy: a rise in PSA of  $>2$  ng/mL above the nadir (per RTOG-ASTRO consensus criteria).
  - 2.1.1.3.5 For patients following radical prostatectomy: 2 absolute PSA values  $> 0.3$  ng/mL (per NCCN guidelines)
  - 2.1.1.3.6 Non-castrate level of testosterone:  $\geq 50$  ng/dL (prior ADT allowed; must be  $\geq 6$  months since last dose of ADT).
  - 2.1.1.3.7 A Pre-Enrollment/Baseline PSADT  $> 3$  months and  $\leq 15$  months
    - 2.1.1.3.7.1 Patients must have  $\geq 3$  PSA measurements over  $\geq 3$  months
    - 2.1.1.3.7.2 The interval between PSA measurements must be  $\geq 4$  weeks
    - 2.1.1.3.7.3 For patients receiving 5-alpha reductase inhibitors (5ARI) e.g. finasteride or dutasteride, only PSA values obtained after at least 3 months on therapy may be used to calculate PSADT.
  - 2.1.1.3.8 Performance Status: ECOG 0-2 or Karnofsky 70-100%
  - 2.1.1.3.9 Life expectancy  $\geq 1$  year.
  - 2.1.1.3.10 Hemoglobin  $\geq 10.0$  gm/dL, WBC  $\geq 2,500/\text{mm}^3$ , ALC  $\geq 500/\text{mm}^3$ , ANC  $\geq 1,000/\text{mm}^3$ , platelet count  $\geq 100,000/\text{mm}^3$ .

- 2.1.1.3.11 PT/PTT  $\leq$  1.5X ULN unless receiving clinically indicated anticoagulant therapy.
- 2.1.1.3.12 SGOT/SGPT  $\leq$  2.5X ULN, total bilirubin  $\leq$  1.5X ULN, Cr  $\leq$  1.5X ULN, estimated GFR (eGFR)  $>$  60 ml/min.
- 2.1.1.4 Hepatitis B and C negative, unless the result is consistent with prior vaccination or prior infection with full recovery.
- 2.1.1.5 HIV negative
- 2.1.1.6 No use of investigational agents within 4 weeks of study enrollment.

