#### **Pre-Enrollment/Baseline and On Study PSADT:**

- PSADT will be calculated using the Memorial Sloan-Kettering Cancer Center cancer information prostate nomogram for PSA doubling time found at:  
<http://www.mskcc.org/mskcc/shared/forms/Nomograms/flash/load.cfm?type=Prostate&width=586&height=505&title=Prostate%20Nomogram>
- Minimum requirements for PSADT include  $\geq 3$  PSA measurements over  $\geq 3$  months.
- The interval between PSA measurements must be  $\geq 4$  weeks.
- For patients receiving 5-alpha reductase inhibitors (5ARI) e.g. finasteride or dutasteride, only PSA values obtained after at least 3 months on therapy may be used to calculate PSADT.
- Calculated PSADT values will be reported in months
- The same laboratory must have performed PSA values used in the calculation of PSADT.
- All PSA values used in the calculation should be  $\geq 0.20$  ng/mL and follow a rising trend although all values need not be consecutively rising.
- All values obtained over a maximum period of 12 months prior to any given protocol time point assessment should be included in the PSADT calculation to reflect the patient's current disease activity.
- PSA values obtained within  $\leq 2$  weeks of instrumentation, documented infection (prostatitis), or radiation proctopathy should be *omitted* from inclusion in PSADT calculations.

On Study PSADT will be calculated at baseline and weeks 12, 24, 36, 48, 60, 72, 84, 96, 108, 120, 132, and 144.

Exploratory comparisons of percent change in PSADT will be done among the following time points:

- Pre-Enrollment/Baseline PSADT vs. Week 3-12 PSADT/
- Pre-Enrollment/Baseline PSADT vs. Week 24 PSADT
- Pre-Enrollment/Baseline PSADT vs. Week 36 PSADT
- Pre-Enrollment/Baseline PSADT vs. Week 48 PSADT
- Week 24 PSADT vs. Week 36 PSADT
- Week 36 PSADT vs. Week 48 PSADT
- Additional exploratory analyses of PSADT will be performed of Pre-Enrollment/Baseline PSADT vs. Weeks 60, 72 and 96 and Week 48 PSADT vs. Weeks 96, 108 and 144 PSADT.

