#### **5.2.2.1 PSADT Response & Failure**

**(assessed in all patients at weeks 12, 24, 36, 48, 60, 72, 84, 96, 108, 120, 132, and 144.)**

- PSADT *response* is defined as:
  - a  $\geq 50\%$  increase in calculated PSADT OR

- a PSADT > 15 months
- Patient's whose PSADT is *decreased* by  $\geq 50\%$  will be considered PSADT *failures*.
- Week 24 PSADT *responders* will be allowed to receive an additional dose of TARP peptide vaccine at Week 36.

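### The PSADT response rule does not visibly class a PSA that stops rising or falls on study, so as written such a man cannot be counted as a response

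*Combined protocol and SAP*

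**What the plan says.** Section 5.2.2 takes PSADT as the "natural logarithm of 2 divided by the slope obtained from fitting a linear regression" of ln(PSA) on time. It states the model behind this: "The PSADT is calculated assuming an exponential increase in serum PSA and first order kinetics". The values used must be at least 0.20 ng/mL and trend upward: "All PSA values used in the calculation should be 0.20 ng/ml or greater and follow an increasing trend".

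The guideline list that follows, under a heading covering both baseline and on-study PSADT, repeats the condition with one relaxation: values must "follow a rising trend although all values need not be consecutively rising". Single dips are therefore allowed, but the overall trend must still rise. The same list asks for at least 3 values over at least 3 months, at least 4 weeks apart, within a maximum of 12 months, all from the same laboratory.

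Section 5.2.2.1 says response and failure are "assessed in all patients at weeks 12, 24, 36, 48" and so on to week 144. Response is a PSADT at least 50% longer, or above 15 months. Failure is a PSADT at least 50% shorter. Section 6.2 makes the percentage meeting the response criteria a secondary endpoint. Sections 3.1 and 5.2.2 add exploratory comparisons of percent change in PSADT between time points.

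**The concern.** The endpoint is meant to detect slower PSA growth after vaccination. The largest effects of that kind are a PSA that stops rising and a PSA that falls. In those cases the formula gives an undefined or negative doubling time, and the rising-trend condition says the calculation should not be made. The plan still assesses every patient, and no visible text says how these men are classed.

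At stake are the secondary response percentage and the percent-change comparisons. A man with a modest slowing can be counted as a response, while a man with a larger effect has no value at the same visit. If the class is settled once results are known, the rate depends on an unplanned decision.

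**Working it through.** The plan gives no figure on this point, so there is none to reproduce. Every PSA course below is assumed.

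**1. Behaviour at zero.** PSADT = ln2/b, with b the ln(PSA) slope per month and ln2 = 0.6931. For b = +0.001, PSADT = +693 months, a response. For b = 0 it is undefined. For b = -0.001 the formula returns -693 months, and the rising-trend condition is not met. A negligible change in slope moves a man from response to no class.

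**2. A falling PSA.** Assume a baseline PSADT of 9 months, PSA halving every 12 months from week 3, and no noise. The response thresholds are 1.5 × 9 = 13.5 months, or more than 15 months.

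*Outside and study values pooled* (outside values at -6 and -3 months, study visits as scheduled, trailing 12 months):

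| Week | Slope b | ln2/b (months) |
|---|---|---|
| 24 | +0.0223 | +31.0, a response |
| 36 | -0.0236 | -29.4, no rising trend |
| 48 | -0.0544 | -12.7, no rising trend |

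Keeping only values at least 4 weeks apart (dropping weeks 3, 9 and 15) gives +30.9, -34.2 and -13.1.

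*Study values only*, if the same-laboratory rule keeps outside values out of the window. Put time in weeks and log2(PSA) on the matching scale: y = t/9 up to week 3, then 3/9 - (t - 3)/12. PSADT in months is then 1/slope.
- Week 12 (weeks 0, 3, 6, 9, 12): y = 0, 0.3333, 0.0833, -0.1667, -0.4167. Sxx = 90 and Sxy = -1.0 - 0.5 - 2.5 = -4.0. Slope = -0.0444, so 1/slope = -22.5.
- Week 24 (adding weeks 15, 18, 24): y = -0.6667, -0.9167, -1.4167. Sxx = 448.875 and Sxy = -31.0625. Slope = -0.0692, so 1/slope = -14.5.

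Pooled, the man is a response at week 24 and has no PSADT by week 36, while his PSA falls throughout. With study values only, he has no PSADT from week 12 on.

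**3. A PSA that only stops rising.** Assume PSA flat from week 3, normal noise with SD 0.10 on ln(PSA), a least-squares slope, and 200,000 simulated patients per cell. At week 48 the slope is non-positive in 38% (baseline PSADT 6 months) and 43% (10 months). The assumed outside values lie beyond 12 months by then, so pooling does not affect these figures. From week 60 the window starts after week 3 (60 - 52 = 8), the true slope in it is zero, and symmetric noise makes about 50% non-positive. One half gets a very long PSADT and the other half none.

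**4. The same rule on the slope scale.** For b > 0 and baseline slope b0 > 0:
- PSADT >= 1.5 × baseline ⇔ b <= b0/1.5
- PSADT > 15 months ⇔ b < ln2/15 = 0.046
- PSADT <= 0.5 × baseline ⇔ b >= 2*b0

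In the example b0 = 0.6931/9 = 0.0770, so the cut-offs are 0.0513, 0.046 and 0.1540. Every slope in the table, and both study-only slopes (-0.0444 × 0.6931 = -0.0308 and -0.0692 × 0.6931 = -0.0480), is a response.

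**The case against.** The strongest objection is that the rule may exist where it cannot be seen. Section 5.2.2 points to Appendix 5, of which only part is visible, and to a nomogram and a published guideline whose handling of a falling PSA is not in the documents. This stands as a limit: the point is that no visible text gives the rule. The visible Appendix 5B worksheets repeat the response definition without covering the case.

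A second objection is that a falling PSA has a home elsewhere. Section 1.1.2.2 names PSA growth and regression rate constants, and an Appendix 5B worksheet has a column for the log slope. Neither is tied to response or failure, so neither settles the class.

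Third, the pooled illustration may break the same-laboratory rule. The documents are not uniform on this: one Appendix 5B window combines outside values with weeks 0 and 3, while others use study values only. That is why both versions are shown. Excluding outside values brings the gap forward.

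Fourth, in the pooled version the man does meet the response definition at week 24. Whether he is lost depends on the visit at which the rate is read, and the documents do not fix one.

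A reader might go further and infer that the plan labels a falling PSA a failure, and so an off-study event, because a negative PSADT is arithmetically more than 50% below baseline. The documents do not support this. It requires ignoring the rising-trend condition, under which no PSADT would be calculated.

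**Conclusion.** The point holds in this form. The formula and the rising-trend condition, followed as written, leave a man with a net flat or falling PSA without a PSADT, so he cannot be counted as a response, although the endpoint is to be assessed in all patients. The size depends on assumed courses: in the worked case the value is missing from week 36 (pooled) or from week 12 (study values only), and for a flat PSA about 38-43% of slopes are non-positive at week 48 and about 50% from week 60. The documents do not show how many men will be affected.

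The inference that such men would be classed as failures is not part of the finding. Nor do the documents say that they would be removed from the denominator; they say only that all patients are assessed. The endpoint is secondary and the time-point comparisons are exploratory. The immunologic response criterion and the two-stage design do not depend on PSADT.

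**What to change.** For the analysis endpoint only, add to Sections 5.2.2 and 6.2:

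- Classify on the ln(PSA) slope b per month against the baseline slope b0. Response: b <= b0/1.5 or b < ln2/15 = 0.046, so zero and negative slopes count as response. Failure: b >= 2*b0.
- Do not use the rising-trend condition to exclude on-study windows, and keep all assessed patients in the denominator.
- Run the time-point comparisons on differences in slope, not percent change in PSADT. In the pooled example, week 48 minus week 36 is -0.0544 - (-0.0236) = -0.0308, which correctly shows a faster fall.
- State whether outside and study values may share a window.
- Keep the 0.20 ng/mL condition, but state in advance how a man is counted if a falling PSA leaves too few values above it. After prostatectomy, entry needs only values above 0.3, and a fall from 0.31 to 0.20 is 1 - 0.20/0.31 = 35%.

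The cost is a few sentences and recalculation from PSA values already collected. The class is unchanged for every positive slope. The downside is that, for non-positive slopes, the analysis label may differ from the one used for dosing or off-study decisions, and the text should say so.

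The off-study criteria in Section 3.6.3 use the same quantity. So do the week-36 dose provisions, where Section 5.2.2.1 relies on the full response definition and the Appendix 1 note gives only the 50% increase. The sponsor must reconcile these; no clinical rule is proposed here.

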#### **Pre-Enrollment/Baseline and On Study PSADT:**

- PSADT will be calculated using the Memorial Sloan-Kettering Cancer Center cancer information prostate nomogram for PSA doubling time found at:  
<http://www.mskcc.org/mskcc/shared/forms/Nomograms/flash/load.cfm?type=Prostate&width=586&height=505&title=Prostate%20Nomogram>
- Minimum requirements for PSADT include  $\geq 3$  PSA measurements over  $\geq 3$  months.
- The interval between PSA measurements must be  $\geq 4$  weeks.
- For patients receiving 5-alpha reductase inhibitors (5ARI) e.g. finasteride or dutasteride, only PSA values obtained after at least 3 months on therapy may be used to calculate PSADT.
- Calculated PSADT values will be reported in months
- The same laboratory must have performed PSA values used in the calculation of PSADT.
- All PSA values used in the calculation should be  $\geq 0.20$  ng/mL and follow a rising trend although all values need not be consecutively rising.
- All values obtained over a maximum period of 12 months prior to any given protocol time point assessment should be included in the PSADT calculation to reflect the patient's current disease activity.
- PSA values obtained within  $\leq 2$  weeks of instrumentation, documented infection (prostatitis), or radiation proctopathy should be *omitted* from inclusion in PSADT calculations.

On Study PSADT will be calculated at baseline and weeks 12, 24, 36, 48, 60, 72, 84, 96, 108, 120, 132, and 144.

Exploratory comparisons of percent change in PSADT will be done among the following time points:

- Pre-Enrollment/Baseline PSADT vs. Week 3-12 PSADT/
- Pre-Enrollment/Baseline PSADT vs. Week 24 PSADT
- Pre-Enrollment/Baseline PSADT vs. Week 36 PSADT
- Pre-Enrollment/Baseline PSADT vs. Week 48 PSADT
- Week 24 PSADT vs. Week 36 PSADT
- Week 36 PSADT vs. Week 48 PSADT
- Additional exploratory analyses of PSADT will be performed of Pre-Enrollment/Baseline PSADT vs. Weeks 60, 72 and 96 and Week 48 PSADT vs. Weeks 96, 108 and 144 PSADT.

#### **5.2.2.1 PSADT Response & Failure**

**(assessed in all patients at weeks 12, 24, 36, 48, 60, 72, 84, 96, 108, 120, 132, and 144.)**

- PSADT *response* is defined as:
  - a  $\geq 50\%$  increase in calculated PSADT OR

- a PSADT > 15 months
- Patient's whose PSADT is *decreased* by  $\geq 50\%$  will be considered PSADT *failures*.
- Week 24 PSADT *responders* will be allowed to receive an additional dose of TARP peptide vaccine at Week 36.

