3.4.1.1 Review of systems and documentation of symptoms

3.4.1.2 Assessment of ECOG Performance Status

3.4.1.3 Vital signs and physical examination

3.4.1.4 Assessment of injection site reactions

3.4.1.5 Provision of Vaccination Report Card to study subject (when TARP vaccine administered)

### 3.4.2 Laboratory Evaluation

(weeks 0, 3, 6, 9, 12, 15, 18, 24, 36, 48, 60, 72, 84, 96, 108, 120, 132, and 144.)

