3.4.2.3 PSA, testosterone

3.4.3 Radiographic Evaluation

(Weeks 0, 48, 96 and 144. No further restaging unless clinically indicated. )

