As stated in Section 3.3.2, an early stopping rule will be used to ensure that the study subjects do not have exposure to excessive toxicity: If more than one of the first nine subjects on a given arm experiences dose limiting toxicity (defined in Section 3.3.1), enrollment will cease for that arm and revisions to the treatment will be discussed with the IRB and FDA. This is because 1/9 has an upper one-sided 90% confidence interval limit of 37%, while 2/9 has an upper one-sided 90% confidence interval limit of 49%; the former would be marginally acceptable as a rate of toxicity while the latter is not. In addition, any unusually severe toxicity noted may result in temporary suspension of accrual pending re-evaluation of the agent. All toxicities noted will be tabulated by type and grade, for each arm. Any such toxicities that appear in at least 5 patients on either arm will also have the distribution of grades of that toxicity compared between the arms using an exact Cochran-Armitage test.

The percent of patients who meet PSADT response criteria as outlined in section 5.2.2 will also be evaluated as a secondary endpoint. In addition, exploratory comparisons of PSADT among study time points will be performed as outlined in Sections 3.1 and 5.2.2. Given that there will be 6 separate comparisons of PSADT, we will only report differences with  $p < 0.01$  as being statistically significant while other differences with  $0.01 < p < 0.05$  will be considered to be trends. Appropriate 95% confidence intervals will be constructed and reported which takes into consideration the two-arm nature of the design. No formal comparison will be undertaken since the study does not have adequate power to address this comparison properly.

It is expected that 1-2 patients per month may be enrolled onto this study. Based on accrual of 18-20 patients per year, accrual should be completed in approximately 2 to 2.5 years if all 40 patients were to be required. To allow for the possibility of inevaluable patients, an accrual ceiling of 43 will be used.

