**Record PSA values with a maximum of 2 digits after the decimal point.**

On Study Sequential PSADT Calculated for Statistical Analysis			
Analysis Window	Study Wk PSA Values Included	Calculated PSADT/Slope Log	Percent Change PSADT
Pre-NIH	Outside PSAs -12 Months to Entry		
-12Months to Week 3	-12 Months plus Wks 0, 3		
Week 0 to Week 3	NIH PSAs only Wks 0, 3		
Week 3 to Week 12	Wks 3, 6, 9, 12		
Week 3 to Week 24	Wks 3, 6, 9, 12, 15, 18, 24		
Week 3 to Week 48	Wks 3, 6, 9, 12, 15, 18, 24, 36, 48		
Week 24 to Week 48	Wks 24, 36, 48		
Week 48 to Week 72	Wks 48, 60, 72		
Week 48 to Week 96	Wks 48, 60, 84, 72, 96		
Week 96 to Week 120	Wks 96, 108, 120		
Week 96 to Week 144	Wks 96, 108, 120, 144		

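### One fixed PSADT response cut is applied from week 12 on, but early PSADTs are much less precise, and the week 3-12 window breaks the plan's own data minimum

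*Combined protocol and SAP*

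**What the plan says.** **Draw schedule.** Section 3.4.2 sets laboratory visits at "weeks 0, 3, 6, 9, 12, 15, 18, 24, 36, 48, 60, 72, 84, 96, 108, 120, 132, and 144", and the panel includes PSA ("3.4.2.3 PSA, testosterone"). Spacing is 3 weeks to week 18, 6 weeks to week 24, and 12 weeks after that.

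**Response rule.** Section 5.2.2.1 counts a man as a responder if he has at least a 50% "increase in calculated PSADT OR" "a PSADT > 15 months". Response is "assessed in all patients at weeks 12, 24, 36, 48, 60, 72, 84, 96, 108, 120, 132, and 144", and the cut is the same at all 12 assessment times.

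**Endpoint.** Section 6.2: "The percent of patients who meet PSADT response criteria as outlined in section 5.2.2 will also be evaluated as a secondary endpoint". It names no time point.

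**Which PSAs enter.** Section 5.2.2 calculates PSADT as ln 2 over the regression slope of ln(PSA) on time, from all values in at most the last 12 months. For baseline and on-study PSADT alike, it requires at least 3 values over at least 3 months, at intervals of at least 4 weeks, from one laboratory. The comparison list in the same section nevertheless names a week 3-12 PSADT against baseline. Appendix 5B, in its table for statistical analysis, lists "Week 3 to Week 12" with the PSAs of weeks 3, 6, 9 and 12, alongside longer windows such as "Week 48 to Week 96".

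**The concern.** The precision of a regression slope depends on how many values there are and how far apart in time they lie. A fixed cut on a noisy PSADT is crossed by chance more often than the same cut on a precise one. If precision improves as the study goes on, a high response percentage at week 12 that fades later can arise with no change in PSA growth. A reader could take that for an early vaccine effect that wears off. The baseline v week 12 comparison in Section 6.2's exploratory set rests on the same early data. Week 12 PSADT is also one of the off-study triggers in Section 3.6.3.

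**Working it through.** **The plan's own figures.** The plan gives no operating figure for PSADT response. Its one related figure, 77% early termination for the immunologic endpoint, reproduces at p0 = 0.10: 0.9^9 + 9 × 0.1 × 0.9^8 = 0.775. (Section 6.2 prints p0 = 0.20 beside it, which would give 43.6%. That is a separate slip.)

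**Step 1: data minimum.** One month is 30.4375/7 = 4.348 weeks.
- Weeks 3-12: 9/4.348 = 2.1 months at 3-week spacing. This fails both the 3-month and the 4-week requirement.
- Weeks 0-12 at nominal dates: 12/4.348 = 2.8 months. This also falls short of 3 months.

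**Step 2: slope precision.** SE(slope) = SD/√Sxx, where Sxx = Σ(t − mean t)², t in months.
- Weeks 3, 6, 9, 12: 2(4.5² + 1.5²) = 45 weeks²; 45/4.348² = 2.4.
- Weeks 3-48, 9 values: 92.3.
- Look-back at week 12, on-study values 0, 3, 6, 9, 12: 2(6² + 3²) = 90 weeks²; 90/4.348² = 4.8.
- Look-back from week 72 on, five 12-weekly values: 2(24² + 12²) = 1440 weeks²; 1440/4.348² = 76.2.

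Weeks 3-48 therefore carry about 39 times the slope information of weeks 3-12, roughly a six-fold difference in SE. The look-back itself is constant from week 72.

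**Step 3: response with no change in PSA growth.** This is a simulation of 100,000 to 200,000 men per scenario. ln(PSA) grows at a constant rate from 48 weeks before entry to week 144, with independent noise. Assumptions not in the documents:
- within-man SD of ln(PSA) from 0.02 to 0.20
- true PSADT lognormal, median 7.5 months, log SD 0.45
- baseline from 5 values over 48 weeks, with observed baseline above 3 and at most 15 months
- a slope at or below zero counts as PSADT above 15 months.

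Appendix 5B windows, percent counted as responders if the cut is applied to them:

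| SD | 3-12 | 3-24 | 3-48 | 48-72 | 48-96 |
|---|---|---|---|---|---|
| 0.02 | 5.1 | 1.6 | 0.8 | 1.6 | 0.9 |
| 0.05 | 18.4 | 4.7 | 1.9 | 5.1 | 2.1 |
| 0.10 | 31.3 | 13.7 | 4.8 | 14.6 | 5.4 |
| 0.20 | 40.7 | 28.1 | 15.0 | 28.8 | 16.1 |

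Twelve-month look-back, on-study PSAs only (percent, rounded):

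| SD | wk 12 | wk 24 | wk 36 | wk 48 on |
|---|---|---|---|---|
| 0.05 | 13 | 4 | 3 | 2 |
| 0.10 | 27 | 13 | 8 | 4-5 |
| 0.20 | 40 | 28 | 21 | 13-16 |

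In an arm of 20 at SD 0.10, weeks 3-12 would give 20 × 0.313 = 6 responders and weeks 3-48 would give 20 × 0.048 = 1.

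**Step 4: is the unequal window the cause?** With every PSADT taken from the same design (3 values, 12 weeks apart), the no-change percentage is flat at 14.5-14.7% for SD 0.10. Unequal data produce the drift; noise sets the level.

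**Step 5: sensitivity at SD 0.10.**
- Look-back thinned to intervals of at least 4 weeks: 29.6, 15.3, 9.3 and 6.1% at weeks 12, 24, 36 and 48, then 4.8-5.4%.
- Pre-enrollment PSAs pooled into the look-back: 3.5, 5.5, 6.5, 5.3 and 4.1% at weeks 12 to 60, then 5.2-5.4%.
- Minimum baseline (3 values over 3 months): 36.1% in weeks 3-12, 22.7% in weeks 3-48.
- Slopes at or below zero excluded: 25.3% and 4.8%.

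**The case against.** **Windows and boosters.** From the 9-to-48-week windows of Appendix 5B, a reader might infer that the responder percentage swings throughout the study, with a dip and rebound around the week 48 and 96 boosters. The documents do not support that. Section 6.2 ties the endpoint to Section 5.2.2, whose look-back is up to 12 months. In Appendix 5B the responder column is in the by-week worksheet; the table of unequal windows records percent change only. Under the look-back the drift lies mainly in weeks 12-36, and from week 72 the data are a constant five PSAs over 48 weeks.

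**Size.** A reader might also infer that false response falls almost to zero in long windows. With a known baseline and a true PSADT of 8 months it runs from 33% (weeks 3-12) to 0.3% (weeks 3-48). Baseline is estimated, however, so about 5% is the realistic low end. With a minimum baseline, all true PSADTs at 9 months and SD 0.20, the Appendix 5B windows are nearly flat at 52-53%.

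**Pooling.** Read literally, all values in the prior 12 months would include pre-enrollment PSAs at week 12, and the drift is then only about 3 points. Appendix 5B even has a pooled row for the 12 months before entry plus weeks 0 and 3. This part stands as a second reading, but the same-laboratory rule argues against pooling outside values.

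**Week-12 span.** Appendix 1 places the entry PSA at screening, up to 14 days early. Counting that value would give 14/4.348 = 3.2 months, so the on-study week-12 shortfall is marginal. The failure of the week 3-12 window is not.

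**Use.** The time-point comparisons are labelled exploratory, no test of responder percentages between periods is planned, and both arms share the schedule. All of this stands, and it limits the point to within-arm trends and early baseline comparisons.

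**Conclusion.** The point holds for the early visits. The week 3-12 PSADT contradicts the plan's own minimum, and the plan leaves open which PSAs define PSADT at weeks 12-36. With on-study PSAs only and SD 0.10, the no-change responder percentage falls from about 27% at week 12 to 4-5% from week 48. The week 3-12 window gives about 31%. The size rests on an assumed SD, a 5-value baseline and mixed true PSADTs. The direction is the same at every SD from 0.02 to 0.20 in that scenario. It largely disappears if pre-enrollment PSAs are pooled. The primary immunologic endpoint and same-week contrasts between arms are untouched.

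The same noise produces false PSADT failures (a fall of at least 50%): 8.6% in weeks 3-12 against 0.0% in weeks 3-48 at SD 0.10. Section 3.6.3 makes such a fall a reason for leaving the study, so early noise could also affect who remains for later percentages.

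**What to change.** 1. Do not report a PSADT response percentage or a baseline comparison from the week 3-12 window or from on-study week-12 values. Reconcile Section 5.2.2 with Appendix 5B so that one window definition gives the PSADT at each time point, and state whether pre-enrollment PSAs may enter.
2. For change over time, fit one mixed model of ln(PSA) to all on-study PSAs with a separate, pre-specified slope per period. Report each slope and its doubling time with a 95% interval.
3. State that differences in responder percentage between weeks 12-36 and later visits will not be read as a vaccine effect.
4. Reconcile the use of week 12 PSADT in Section 3.6.3 with the minimum-data rule in Section 5.2.2.

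Equal 24-week windows of three PSAs would also remove the drift, but they are a poorer trade. At SD 0.10 they hold the no-change percentage at about 15% throughout, against about 5% from week 48 under the look-back, and they give up the 12-month rule.

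The cost is SAP wording, a little more analysis, and the loss of the week-12 response percentage. No new PSA draws are needed.
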